
DATA COLLECTION & ANALYSES
	
Descriptive statistics will be performed using data collected from the health questionnaire and measures obtained from the medical testing. Demographic data of participants will be compared to 1996 Canadian census data to determine the extent in which the survey results can be generalized to the Port Colborne community. Response rates will be estimated across geographical regions of Port Colborne to evaluate the potential for response bias. Prevalence rates for selected health conditions will be summarized for the Port Colborne area, and where sample size permits, the rates will be compared across stratified sampling areas. Similarly, the occurrence of selected health conditions in Port Colborne will be compared to participants of the Canadian Community Health Survey, a recently conducted national health survey. Tests of significance, including confidence intervals will be presented for these comparisons. Multivariate methods will be used to adjust for differences in age and sex of the comparison populations.
 
Levels of the individual Chemicals of Concern, as determined by biological specimens analysis, will also be summarized. Variations in exposure levels within Port Colborne will be explored by calculating descriptive statistics, and through the use of multivariate analysis of variance methods. Logistic regression will be used to evaluate the relationship between the selected health conditions and exposure to Chemicals of Concern from both biological specimens and relevant questionnaire items of the health questionnaire. These models will provide odds ratios that will be adjusted for the effects of other potential confounding variables, such as age, sex, smoking habits, alcohol use and other indicators of socio-economic status. In addition, multivariate analysis of variance will be used to compare laboratory measures of Chemicals of Concern taken in Port Colborne residents to a normative sample, while adjusting for age and sex.

Abbreviations

ATSDR	Agency for Toxic Substances and Disease Registry
CBRA	Community-Based Risk Assessment
CCHS	Canadian Community Health Survey
CDC	Center for Disease Control
CHAP	Community Health Assessment Project
CO	Carbon Monoxide
COHb	Carboxyhaemoglobin
CoCs	Chemicals of Concern
CRF	Case Report Form
DLC	Differential Leukocyte Count
ECG	Electrocardiogram
ft4	Free Tetraiodothyronine (Thyroxine)
FEV1	Forced Expiratory Volume in 1 Second
FVC	Forced Vital Capacity
Hb	Haemoglobin

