6.4 Statistical Analysis

The frequency distributions of variables collected within the health questionnaire and medical tests will be tabulated. The number of missing responses for each variable will be presented, and where possible, these missing values will be treated as a separate category. Particular attention will be given to examining response rates for income levels, since this variable will be used as a proxy to socioeconomic status. If necessary, other factors, such as education, may need to be used instead.

Prevalence rates for health conditions will be calculated by age-group for males and females. Statistically significant differences across strata will be evaluated by using the Chi-Square and likelihood ratio tests for categorical data, and the Student's t-test for continuous data. Multivariate analysis of variance will be used to adjust comparisons for the influence of potential confounding variables. Comparisons will need to take into account possible differences in the age and sex structure of the populations being compared. Of particular interest will be the comparison of Area 3 (otherwise known as the Rodney Street area) to the rest of Port Colborne. Comparisons will also be made to reference data for Ontario or other normative data.

To evaluate the potential influence for response bias, where possible, socio-economic characteristics will be compared between non-respondents and participants. These variables will include: age, sex, family size, income level, and neighborhood of residence. Statistical tests of significance will be performed to determine whether non-responders differed from those who participated in the survey. Response bias will also be examined by comparing survey results obtained from the 1996 Canadian census data.

The prevalence of selected health characteristics will be compared to responses obtained from participants of the 2000 CCHS. In order to control for differences in the underlying populations, direct standardization will adjust for the age and gender make-up of the populations being compared. The ratio of these standardized rates will be calculated, and

95% confidence intervals of this ratio will be used to assess statistically significant differences.

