Univariate statistics will be calculated for each chemical, as determined by laboratory analysis, to summarize the levels of the CoCs. These statistics will include: the mean, median, range, standard deviation and upper and lower percentiles. Tests for normality will be conducted to determine whether transformations of the CoCs values may be necessary for some multivariate modeling procedures. Variations in exposure levels within Port Colborne will be explored by calculating these summary statistics separately across different areas within the city. Differences across regions will be evaluated using multivariate regression analyses. Lognormal transformations are frequently applied to exposure distributions that are skewed. For CoCs with a large number of non-detectable levels, logistic regression analysis will be used to model those with exposure above the median CoCs level, relative to those with exposure below the median value.

Logistic regression methods will be used to evaluate the relationship between exposure to CoCs and selected health conditions. Because exposure to CoCs has been measured using two instruments (i.e., biological specimens and health questionnaire items), logistic regression analysis will be performed using these two series of independent variables. Pearson correlations coefficients and categorical analyses will be used to examine the concordance between the exposure measures from the laboratory and the summary measure estimated from the questionnaire.

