The logistic regression model will provide a parameter estimate that can be readily transformed into an odds ratio. This odds ratio provides a measure of risk that can be used to determine whether those with high levels of exposure to CoCs are more likely to have a specified health condition. Survey participants will be categorized into tertiles based on their clinical exposure measurements and into binary groups based on the answers they give to the exposure question in the health questionnaire. Risk estimates will be calculated by comparing the prevalence of disease among those in the highest tertile of exposure to those in the lowest and for those indicating exposure in their answers to the questionnaire versus no exposure. The 95% confidence intervals for these odds ratios will also be calculated. This confidence interval can be used to determine whether or not the association may be due to chance. These estimates of risk will be adjusted for the potential confounding influence of other relevant variables, such as age, sex, smoking habits, alcohol use, and indicators of socio-economic status. All statistical analyses will be conducted by using SAS. The fit of the model will be assessed by using the Hosmer-Lemeshow goodness of fit statistic.

Multivariate analysis of variance will be used to compare laboratory measures of CoCs taken in Port Colborne residents to a normative sample. These multivariate models will be adjusted by age and sex of the subjects. Differences between the two populations will be evaluated by using the F-test statistics generated from the ANOVA model. Where necessary, measured levels of CoCs will be transformed in order to ensure that assumptions of normality are satisfied. If this assumption cannot be met through a

transformation, than non-parametric methods (e.g., Wilcoxon Rank Sum test) will be considered.

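### The only non-parametric fallback named for comparing metal levels with a normative sample, the Wilcoxon rank sum test, does not carry the age and sex adjustment the protocol requires for that comparison

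*Protocol*

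**What the plan says.** The last paragraph of section 6.4 states the comparison: "Multivariate analysis of variance will be used to compare laboratory measures of CoCs taken in Port Colborne residents to a normative sample". It then states the adjustment, "These multivariate models will be adjusted by age and sex of the subjects", and the test, "Differences between the two populations will be evaluated by using the F-test statistics generated from the ANOVA model". The synopsis (Data Collection & Analyses) describes the same comparison as one made "to a normative sample, while adjusting for age and sex". Earlier in 6.4 the requirement is put generally: "Comparisons will need to take into account possible differences in the age and sex structure of the populations being compared".

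Non-normality is handled in two steps. Metal levels are transformed where necessary. Only if the assumption still cannot be met does the plan say "transformation, than non-parametric methods (e.g., Wilcoxon Rank Sum test) will be considered". No stratified, standardised or covariate-adjusted version of the test is mentioned.

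The comparisons between areas of the city are described separately. Section 6.4 uses multivariate regression for them. Mock Table 9 specifies ANOVA, and mock Table 12 logistic regression, both controlling for age and sex. No rank test is stated as a fallback for these.

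**The concern.** The adjusted model and the rank sum test address different null hypotheses. The adjusted model asks whether levels differ between the two populations at the same age and sex. The rank sum test asks whether the crude distributions are the same. If the populations differ in age or sex structure, and levels vary with age or sex, the second null is false even when the first is true.

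Nothing in the protocol suggests that a normative sample would match the study sample. Participants are 12 or older, the Rodney Street area is deliberately oversampled, and section 4.1 acknowledges self-selection. The protocol itself sees the need to adjust.

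An age or sex difference could therefore be reported, to a community already worried about contamination, as a difference in metal burden. An imbalance in the other direction could hide a real difference. A metal analysed by the crude test would also not be comparable with one analysed by the adjusted model.

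**Working it through.** There is no figure in the protocol to reproduce, so the mechanism was checked by simulation.

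**From the protocol:** 1,000 Port Colborne participants (section 6.1.1); adjustment for age and sex (synopsis and 6.4); 5% type I error (stated in 6.1.1 for the area comparison, taken here as two-sided).

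**Assumed, because the protocol does not give them:** the size of the normative sample, the age and sex imbalance, and the dependence of metal levels on age and sex.

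**Model.** The level, on a transformed scale with residual SD 1, depends on age and sex and has no group effect. The crude shift between groups created by imbalance alone is

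shift = (age effect per SD of age) × (age gap in SDs) + (sex effect) × (difference in the proportion of one sex).

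**Setting A: heavy-tailed errors (t with 3 df), age SD 18 years, 1,000 runs per cell.** The table gives the rejection rate of the plain Wilcoxon test for three pairs of group sizes.

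| Imbalance and effects | Shift | 1,000 v 1,000 | 1,000 v 300 | 500 v 500 |
|---|---|---|---|---|
| Balanced; effects 0.3 | 0 | 5% | 5% | 6% |
| 5 years and 5 points of sex; effects 0 | 0 | 5% | 5% | 5% |
| 5 years and 5 points; effects 0.1 | 0.1×5/18 + 0.1×0.05 = 0.033 | 17% | 10% | 12% |
| 3 years; effects 0.3 | 0.3×3/18 = 0.050 | 27% | 15% | 15% |
| 5 years and 5 points; effects 0.3 | 0.3×5/18 + 0.3×0.05 = 0.098 | 75% | 45% | 44% |
| 10 years; age effect 0.3 only | 0.3×10/18 = 0.167 | 100% | 87% | 90% |

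On the same data, three methods that keep age and sex rejected in about 4% to 6% of runs in every cell: ANCOVA on the values, ANCOVA on the ranks, and a van Elteren test stratified by age band and sex. With 1,000 runs, the simulation standard error at 5% is √(0.05×0.95/1,000) = 0.7 percentage points, so these are nominal within error.

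**Setting B: normal errors on the log scale, lowest 10% of values set to the detection limit, 600 runs per setting.** Age gap 0.3 SD, age effect 0.2 per SD, sex effect 0.5, with 1,000 v 1,000:

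- no sex imbalance: shift 0.2×0.3 = 0.060, Wilcoxon rejects in 24%;
- 5-point sex imbalance: shift 0.060 + 0.5×0.05 = 0.085, rejects in 45% (26% at 500 v 500);
- 10-point sex imbalance: shift 0.060 + 0.5×0.10 = 0.110, rejects in 63%.

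With effects half that size and a 0.2-SD age gap, the rate was about 9%. Adjusted models on the values or on the ranks stayed at about 5% to 7%.

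The two settings agree. The plain test holds its level when the shift is zero. Once there is a shift, the error rate rises with the shift and with the sample size. Keeping age and sex in the analysis removes the excess.

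**The case against.** Several stronger readings are tempting, and the protocol does not support them.

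- *Any metal that fails a normality test loses its adjustment.* The normality tests have a narrower purpose: "Tests for normality will be conducted to determine whether transformations of the CoCs values may be necessary for some multivariate modeling procedures". Transformation comes next, and the non-parametric step follows only if that fails. No particular test or threshold is named as the switch.
- *The protocol commits to an unadjusted test.* Wilcoxon is given as an example of methods that will be considered. An adjusted rank method would also fit the sentence and would agree with the general requirement in 6.4.
- *The fallback will be used often because many values will be below the detection limit.* For CoCs with many non-detects, 6.4 provides a logistic model for levels above versus below the median, which can include age and sex. That provision sits in the paragraph on differences within the city and is not carried over to the normative comparison. How often the fallback would be reached is therefore unknown.
- *The problem affects every two-group comparison.* The clause belongs to the normative-sample comparison alone. The area comparisons use regression or models adjusted for age and sex.

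Two further objections bear on the point itself. The first is that the choice of rank method belongs in the statistical analysis plan, which is not to hand. That has some force, but the protocol does not leave the method unnamed. It names one, and that one cannot meet the adjustment stated in the same paragraph. The second is that adjusted methods need person-level normative values with age and sex, and the protocol identifies no such dataset. That is true, but the planned adjusted model needs the same data, so the remedy adds no requirement.

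**Conclusion.** The point holds in a limited form. For the comparison of CoC levels with a normative sample, the one fallback named does not adjust for age and sex, although the synopsis and section 6.4 both require it. If that test is used, and the populations differ in age or sex on which levels depend, it can reject with no difference at fixed age and sex.

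The size rests wholly on assumptions about imbalance, effects and the normative sample. There is no inflation if groups are balanced or levels are unrelated to age and sex. False rejection is about 9–17% under mild assumptions, and 24–75% under moderate ones at 1,000 v 1,000, with lower rates in the smaller samples. The area comparisons within the city are unaffected. This should be corrected, but it is a flaw in a contingent clause and not in the main model.

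**What to change.** In the last paragraph of section 6.4, replace the Wilcoxon example with a fallback that keeps age and sex. Two suitable choices are rank ANCOVA (ranks regressed on group, age and sex) and a van Elteren test stratified by age-sex group. For CoCs with many non-detects, name either a censored lognormal regression or the median-split logistic model already in 6.4, with age and sex included, and state that it applies to the normative comparison too.

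The cost is one or two sentences and a few lines of SAS. The methods need only the individual levels, ages and sexes that the planned adjusted model already requires. The downside is a slightly less familiar test.

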6.5 Results

The results proposed in the statistical analysis section will be summarized with the use of mock tables.

6.5.1 Mock Tables

Table 1.
Response Rates, by Sampling Areas,
CHAP Comprehensive Health Questionnaire, Fall 2002

Total Number of Randomly Selected Households
Total Number of Questionnaire Refusals
Refusals from Area 1
Refusals from Area 2
Refusals from Area 3
Refusals from Area 4
Refusals from Area 5
Overall Questionnaire Response Rate
Total Number of Biological Testing Refusals
Refusals from Area 1
Refusals from Area 2
Refusals from Area 3
Refusals from Area 4
Refusals from Area 5
Overall Biological Testing Response Rate

Table 2.
Demographic Characteristics of Participants, by Sampling Areas,
Compared to Census Data
CHAP Comprehensive Health Questionnaire, Fall 2002

Characteristic	Area 3	1996 Census Data for Area 3	Areas 1, 2, 4, 5	1996 Census Data for Areas 1, 2, 4, 5
	N (%)	N (%)	N (%)	N (%)
Sex				
Female				
Male				
Age				
0 - 14				
15 - 19				
20 - 24				
25 - 54				
55 - 64				
65 - 74				
≥ 75				
Mean				
Mean Household Size				
Household Income				
< \$20 000				
\$20 000 to less than 40 000				
\$40 000 to less than 60 000				
\$60 000 to less than 80 000				
≥ \$ 80 000				
Education				
Less than high school				
High School				
Post Secondary				
Ethnic Background				
Caucasian				
Oriental				
Native				
Other				
Marital Status				
Married/Common-law				
Single				
Divorced/Separated				
Widowed				

categorized by standard thresholds

Table 3.
Demographic Characteristics of Participants, by Sampling Areas,
CHAP Comprehensive Health Questionnaire, Fall 2002

Characteristic	Area 3	Areas 1, 2, 4, 5	Total for Port Colborne	p-value [†]
	N (%)	N (%)	N (%)	
Sex				
Female				
Male				
Age				
0 – 14				
15 - 19				
20 - 24				
25 - 54				
55 - 64				
65 - 74				
≥ 75				
Mean				
BMI				
Underweight [‡]				
Average [‡]				
Overweight [‡]				
Obese [‡]				
Mean				
Mean Household Size				
Household Income				
< \$20 000				
\$20 000 to less than 40 000				
\$40 000 to less than 60 000				
\$60 000 to less than 80 000				
≥ \$ 80 000				
Education				
Less than high school				
High School				
Post Secondary				
Ethnic Background				
Caucasian				
Oriental				
Native				
Other				
Marital Status				
Married/Common-law				
Single				
Divorced/Separated				
Widowed				
Years lived in Port Colborne				
< 5				
5 - <10				
10 - <20				
20+				

[†] p-value is based on Chi-square for comparison of proportions, likelihood ratio test for categorical variables and t-test for comparison of means.

[‡] categorized by standard thresholds

Table 4.
Lifestyle and Dietary Information of Participants, by Sampling Areas,
CHAP Comprehensive Health Questionnaire, Fall 2002

	Area 3	Areas 1, 2, 4, 5	Total for Port Colborne	p-value [†]
	N (%)	N (%)	N (%)	
Occupation related to Exposure *				
Yes				
No				
Primary Source of Drinking Water				
Municipal				
Well				
Bottled				
Gardening Activity				
Yes				
No				
Non-occupational Activities related to Exposure to CoCs **				
Yes				
No				
Cigarette smoking status				
Never				
Current				
Former				
Unknown				
Exposure to second-hand Smoke				
Never				
As a child only				
As an adult only				
As a child and adult				
Current alcohol consumption				
Less than once a month				
1 To 3 times a month				
4 to 12 times a month				
> 12 times a month				
Jewelry piercings				
Yes				
No				

* Includes the following occupations: mining; metal cutting, grinding and refining; smelting; foundry work; steel making; welding; plumbing; brazing; plumbing; shipbuilding; metal plating or electroplating; boiler maker/repairer

** Includes painting, renovations, landscaping and automotive work

† p-value is based on Chi-square for comparison of proportions.

Table 5.
Prevalence of Selected Health Conditions of Participants, by Sampling Areas,
CHAP Comprehensive Health Questionnaire, Fall 2002

	Area 3	Areas 1, 2, 4, 5	Total for Port Colborne	p-value [†]
	N (%)	N (%)	N (%)	
Chronic Bronchitis				
Emphysema / Chronic Obstructive Pulmonary Disease				
Other Allergies				
Asthma				
Hypertension				
Heart Disease				
Thyroid Condition				
Stomach / Intestinal Ulcers				
Gastroenteritis				
Peripheral Neuropathy				
Arthritis				
Parkinson's				

[†] p-value is based on Chi-square for comparison of rates from Area 3 to Areas 1, 2, 4, and 5 after adjustment for differences in the age and sex distribution of the two populations.

Table 6.
External Comparison of Selected Health Conditions of Participants, by Sampling Areas,
CHAP Comprehensive Health Questionnaire, Fall 2002

	Port Colborne	Ontario	p-value [†]
	Prevalence	Prevalence	
Chronic Bronchitis			
Emphysema / Chronic Obstructive Pulmonary Disease			
Food Allergies			
Other Allergies			
Asthma			
Dermatitis			
High Blood Pressure			
Heart Disease			
Anaemia			
Thyroid Condition			
Stomach / Intestinal Ulcers			
Gastroenteritis			
Jaundice			
Parkinson's Disease			
Peripheral Neuropathy			
Parkinson's			

[†] p-value is based on Chi-square statistic of rates after direct standardization by age and sex. .

Table 7.
Comparison of the Mean Levels of Selected Biological Measures, by Sampling Areas,
CHAP Comprehensive Health Questionnaire, Fall 2002

	Area 3	Areas 1, 2, 4, 5	Total for Port Colborne	p-value [†]
	Mean (s.d)*	Mean (s.d)	Mean (s.d)*	
Haemoglobin				
White Blood Cell Count				
Red Blood Cell Count				
Haematocrit				
Mean Cell Volume of Red Cells				
Mean Hemoglobin Concentration of Red Cells				
Platelet Count				
Red Cell Distribution Width				
Mean Platelet Volume				
Differential Leukocyte Count				
Bilirubin				
Creatinine				
Plasma Cotinine				
Plasma Screen for Concentration of TSH				
Blood Urea Nitrogen				

[†] p-value is based on an ANOVA for comparing the means between Area 3, and Areas 1, 2, 4, and 5; after adjusting for difference in the age and sex distribution of the two populations.

* s.d. = standard deviation

Table 8.
Comparison of the Non-Specimen Tests Among Participants, by Sampling Areas,
CHAP Comprehensive Health Questionnaire, Fall 2002

	Area 3	Areas 1, 2, 4, 5	Total for Port Colborne	p-value [†]
	Mean (s.d) [*]	Mean (s.d)	Mean (s.d.)	
Calculated BMI				
Electrocardiogram	---	---	---	---
Blood Pressure				
Carbon Monoxide Breath Test				
Forced Expiratory Volume in 1 second				
Forced Vital Capacity				
Peak Expiratory Flow Rate				
Dermatology Patch: Nickel Sulfate				
Dermatology Patch: Cobalt Dichloride				

[†] p-value is based on an ANOVA for comparing the means between Area 3, and Areas 1, 2, 4, and 5; after adjusting for difference in the age and sex distribution of the two populations.

^{*} s.d. = standard deviation

Table 9.
Comparison of the Selected Measures of Chemicals Among Participants, by Sampling Areas, CHAP Comprehensive Health Questionnaire, Fall 2002

	Area 3	Areas 1, 2, 4, 5	Total for Port Colborne	p-value [†]
Chemical	Mean (s.d) [*]	Mean (s.d)	Mean (s.d)	
Nickel (Urine)				
Copper (Urine)				
Cobalt (Urine)				
Arsenic (Urine)				
Mercury (Urine)				
Lead (Blood)				

[†] p-value is based on an ANOVA for comparing the means between Area 3, and Areas 1, 2, 4, and 5; after adjusting for difference in the age and sex distribution of the two populations.

^{*} s.d. = standard deviation

Table 10.
Comparison of the Proportion of Tests Outside Normal Range for Selected Biological Measures,
by Sampling Areas,
CHAP Comprehensive Health Questionnaire, Fall 2002

	Area 3	Areas 1, 2, 4, 5	Total for Port Colborne	p-value [†]
Proportion Outside Normal Range				
Haemoglobin (normal range)				
White Blood Cell Count (normal range)				
Red Blood Cell Count (normal range)				
Haematocrit (normal range)				
Mean Cell Volume of Red Cells (normal range)				
Mean Hemoglobin Concentration of Red Cells (normal range)				
Platelet Count (normal range)				
Red Cell Distribution Width (normal range)				
Mean Platelet Volume (normal range)				
Differential Leukocyte Count (normal range)				
Bilirubin (normal range)				
Creatinine (normal range)				
Plasma Cotinine (normal range)				
Plasma Screen for Concentration of TSH (normal range)				
Blood Urea Nitrogen (normal range)				

[†] p-value is based on logistic regression analysis controlling for differences in the age and sex distribution of the two sampling areas

Table 11.
Comparison of the Proportion of Non-specimen Tests Outside Normal Range, by Sampling Areas, CHAP Comprehensive Health Questionnaire, Fall 2002

	Area 3	Areas 1, 2, 4, 5	Total for Port Colborne	p-value [†]
Proportion Outside Normal Range				
Calculated BMI (average range)				
Electrocardiogram [‡]				
Blood Pressure (normal range)				
Carbon Monoxide Breath Test (normal range)				
Forced Expiratory Volume in 1 second (normal range)				
Forced Vital Capacity (normal range)				
Peak Expiratory Flow Rate (normal range)				
Dermatology Patch: Nickel Sulfate (normal range)				
Dermatology Patch: Cobalt Dichloride (normal range)				

[†] p-value is based on logistic regression analysis controlling for differences in the age and sex distribution of the two sampling areas

[‡] proportion with abnormal electrocardiogram

Table 12.
Comparison of the Proportion of Chemical Measures Outside Normal Range, by Sampling Areas, CHAP Comprehensive Health Questionnaire, Fall 2002

	Area 3	Areas 1, 2, 4, 5	Total for Port Colborne	p-value [†]
	Proportion Outside Normal Range			
Nickel (Urine) (normal range)				
Copper (Urine) (normal range)				
Cobalt (Urine) (normal range)				
Arsenic (Urine) (normal range)				
Mercury (Urine) (normal range)				
Lead (Blood) (normal range)				

[†] p-value is based on logistic regression analysis controlling for differences in the age and sex distribution of the two sampling areas.

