In addition to the weighting that adjusts for the oversampling in the Rodney Street area, it may be necessary to make adjustments to the sample if there are more people in one demographic category or other grouping than there should be, based on the real or true distribution of these groups in the population. Using available census data, combined with the observable demographic characteristics of the created sample, mathematically-derived weighting formulas will be considered to put the final, weighted sample in line with what it should be based on the characteristics of the population. Although many mathematical adjustments are rarely required to bring a sample into line with the real distribution characteristics of a population, most studies involving large samples do require a re-weighting to some degree.

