 - ___ Trades certificate or diploma from a vocational school or apprenticeship training
 - ___ Non-university certificate or diploma from a community college, CEGEP, school of nursing, etc.
 - ___ University certificate below bachelor's level
 - ___ Bachelor's degree
 - ___ University certificate or diploma above bachelor's degree

10. Can you estimate in which of the following groups your household income falls? 

ADULT

Was the total household income ...

- Less than \$20, 000?
 - Less than \$10, 000?
 - Less than \$5, 000?
 - \$5, 000 or more?
 - \$10, 000 or more?
 - Less than \$15, 000?
 - \$15, 000 or more?
- \$20, 000 or more?
 - Less than \$40, 000?
 - Less than \$30, 000?
 - \$30, 000 or more?
 - \$40, 000 or more?
 - Less than \$50, 000?
 - \$50, 000 to less than \$60, 000?
 - \$60, 000 to less than \$80,000?
 - \$80, 000 or more?
- No Income

Residential Information

11. Please fill in the following table for your current and all past residences in Port Colborne.

Address ¹	Period of Stay ²		Type of Dwelling ³	Age of Residence ⁴
	From	To		

¹Please indicate street address, city, province, country, and postal code.

²Please indicate from MM/YYYY to MM/YYYY.

³Please indicate one of the following:

- Single Detached House
- Semi-Detached or Double (side-by-side)
- Garden House, Town-House or Row House
- Duplex (one above the other)
- Low-rise apartment (less than 5 stories)
- High-rise apartment (5 or more stories)
- Institution
- Collective dwelling (such as a Hotel/Motel, Rooming or Boarding House)
- Mobile home
- Farm or Acreage
- Other (please specify _____)

⁴Please indicate number of years.

12. If you have resided or are residing in more than one home concurrently, please fill in the following table: CHILD

Address	Percentage of Time Spent
#1	
#2	

Occupational Information

13. a) Do you now or have you ever worked in one of the following industries/occupations: Y/N ADULT.

b) If yes, please specify which industry/occupation:

- | | |
|--------------------------------|-----------------------------------|
| 1 - Underground mining | 8 - Welding |
| 2 - Smelting | 9 - Brazing |
| 3 - Metal Refining | 10 - Sintering |
| 4 - Foundry work | 11 - Plumbing |
| 5 - Steelmaking | 12 - Metal plating/electroplating |
| 6 - Metal Cutting and grinding | 13 - Shipbuilding/breaking |
| 7 - Boiler maker/repairer | 14 - Lumberyard/Sawmill |

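### Mock Table 2 compares fall 2002 household income with 1996 census income in the same dollar bands, with no adjustment for the difference in dollar years

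*Protocol*

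**What the plan says.** Mock Table 2 (protocol section 6.5.1) is titled "CHAP Comprehensive Health Questionnaire, Fall 2002". It gives participants by area and, beside them, columns headed "1996 Census Data for Area 3" and "1996 Census Data for Areas 1, 2, 4, 5". One set of household-income rows serves all four columns: below $20,000, then bands such as "20 000 to less than 40 000", up to $80,000 or more. No dollar year, index or conversion is stated.

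The participant figure comes from question 10 of the questionnaire (Appendix 10.1), an adult item: "Can you estimate in which of the following groups your household income falls". It also uses fixed dollar groups and states no reference year.

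The comparison has a stated purpose:

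- **Synopsis:** "Demographic data of participants will be compared to 1996 Canadian census data to determine the extent" to which the results can be generalized to the community.
- **Section 4.1:** it treats as critical the question of whether non-response is linked to a characteristic such as socio-economic status, and says census data can be used to answer it.
- **Section 6.4:** "Response bias will also be examined by comparing survey results obtained from the 1996 Canadian census data". The same section makes income the proxy for socio-economic status, with education as the fallback if needed.
- **Section 6.2.1.1:** income is among the demographic items to be used for adjusting the data if the sample differs from the population.
- **Section 4.1, on weighting:** "mathematically-derived weighting formulas will be considered to put the final, weighted sample in line" with the population.

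The protocol's only caution about the age of the 1996 census, in section 6.1.1, concerns the dwelling and population counts in its Table 2. It does not mention income.

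**The concern.** Sex, age, education and marital status can be tabulated against an older census without a change of unit. Income cannot. A dollar band holds a different part of the income distribution once nominal incomes have moved, so the survey and census columns are on different scales although the row labels match.

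At stake is the reading of the one socio-economic row measured in dollars. Growth in nominal income moves households into higher bands, so a representative sample could be reported as self-selected towards better-off households. The shift can also work the other way: real over-representation of low-income households could be partly cancelled by income growth and go unseen. If income were later used in census-based weights, the same error would enter the weights.

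**Working it through.** The plan gives no figure for this comparison, so there is nothing to reproduce. The check asks how far the bands would shift for a fully representative sample.

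**Inputs from the protocol.** Band limits of $20,000, $40,000, $60,000 and $80,000 (mock Table 2). Participant income dated fall 2002, reference income from the 1996 census.

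**Assumptions, none of them in the documents.** Household income at the census is lognormal with median m of $35,000, $40,000 or $45,000 and log-SD s of 0.7 or 0.8. Every income is multiplied by (1 + g) by the survey date, with g from 5 to 20%.

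**Formulas.** With Φ the standard normal distribution function:

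- share at $80,000 or more = 1 − Φ(ln(80,000 / (m(1 + g))) / s)
- share below $20,000 = Φ(ln(20,000 / (m(1 + g))) / s)

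Setting g = 0 gives the census column.

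**Worked example, m = $40,000, s = 0.7, g = 15%** (survey median 40,000 × 1.15 = $46,000):

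| Band | Census column | Survey column | Change |
|---|---|---|---|
| $80,000 or more | 1 − Φ(ln(80/40)/0.7) = 1 − Φ(0.990) = 16.1% | 1 − Φ(ln(80/46)/0.7) = 1 − Φ(0.791) = 21.5% | +5.4 points |
| Below $20,000 | Φ(ln(20/40)/0.7) = Φ(−0.990) = 16.1% | Φ(ln(20/46)/0.7) = Φ(−1.190) = 11.7% | −4.4 points |

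**Range over all six combinations of m and s:**

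| Growth g | Rise in share at $80,000 or more | Fall in share below $20,000 |
|---|---|---|
| 0% | 0 | 0 |
| 5% | 1.4 to 2.0 points | 1.4 to 2.0 points |
| 10% | 2.9 to 4.1 points | 2.6 to 3.7 points |
| 15% | 4.4 to 6.1 points | 3.6 to 5.3 points |
| 20% | 6.0 to 8.2 points | 4.5 to 6.7 points |

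**If income were used for weighting.** A weight that forces the sample back to the census share is the census share divided by the survey share. In the worked example that is 16.1/21.5 = 0.75 for the top band and 16.1/11.7 = 1.38 for the bottom band. Every correct weight would be 1.00.

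The effect on an overall prevalence is much smaller. Take m = $40,000, s = 0.7 and an assumed gradient of 8, 6.5, 5, 4.5 and 4% from the lowest to the highest band. The true overall prevalence is then 5.60% at 10% growth and 5.45% at 20% growth, and weighting to the old bands gives 5.77% in both cases. The errors are 5.77 − 5.60 = 0.17 and 5.77 − 5.45 = 0.32 points. Section 6.1.1 aims to measure asthma prevalence to within 2 points.

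**After the fix.** On a common dollar basis (equivalent to g = 0), a representative sample shows no shift in any band and all weights are 1.00.

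**The case against.** The strongest reply is that this is an empty table shell, and that the dollar year of a benchmark column is a footnote that an analysis plan could supply. That lowers the weight of the point but does not remove it. The protocol fixes the comparator year and the bands, and following them as written gives a mis-scaled row.

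Other parts of the reply stand and limit the claim:

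- **No significance test is specified.** A reader might infer that the check would formally reject a representative sample. Mock Table 2 has no p-value column, and the tests promised in section 6.4 concern non-respondents versus participants. A false-rejection rate would therefore describe a test that is not in the plan.
- **Weighting on 1996 income is not planned.** A reader might infer that the sample will be re-weighted to the old bands. Section 4.1 only says formulas will be considered, and names neither income nor a census year in that statement. Section 6.2.1.1 does include income, but its target is the true population distribution. The Ontario comparison is specified as direct standardization by age and sex.
- **There are other safeguards.** Section 6.4 plans, where possible, to compare income between non-respondents and participants, which does not depend on census dollars. The education row of mock Table 2 is also unaffected. It would be too strong to say that a real loss of low-income households could not be detected.
- **The direction depends on growth in nominal income,** for which the documents give no figure.

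**Conclusion.** The point holds as a scaling error in one row of the representativeness check. Survey and census income are set side by side in unadjusted dollars of different years, and that row carries the protocol's chosen marker of socio-economic status. Under the assumptions above, growth of 10 to 20% would make a representative sample appear to have about 3 to 8 points too many households at $80,000 or more and about 2.5 to 7 points too few below $20,000. At 5% growth the top-band shift is about 1 to 2 points, and with no growth it is nil.

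The documents do not support a claim that prevalence estimates will be materially biased. Income weighting is possible rather than planned, and its effect on overall prevalence is probably small: about 0.2 to 0.3 points in the illustration. The unweighted comparison of Area 3 with the rest of Port Colborne uses survey-date income on both sides and is unaffected. The correction is worth making because it is cheap, and it should be made before representativeness is judged or any weights are built.

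**What to change.** In mock Table 2 and section 6.4, state that census household income will be put on the survey's dollar basis before the columns are compared. Either restate the census band limits in survey-year dollars with a published price or income index, or compare relative position in the income distribution of the same year. Give the index and the dollar years in a footnote to the table.

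If neither can be done, leave income out of the census response-bias check and out of any census-based weights, and use education for both. Section 6.4 already names education as the substitute, and mock Table 2 already tabulates it.

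The cost is a footnote, a sentence and some recoding. The downside is slight imprecision from interpolating within the census bands.
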